Clinical Trial Protocol: THR-1442-C-443

Study Title: A Phase 1, Open-label, Randomized, Two-period, Two-treatment, Crossover Study to Evaluate the Effect of Bexagliflozin on the Pharmacokinetics of Digoxin in Healthy Subjects

Study Number: THR-1442-C-443

Study Phase: 1

Product Name: Bexagliflozin Tablets, 20 mg

Indication: Type 2 Diabetes Mellitus

Investigators: Single Center

Sponsor: Theracos Sub, LLC

Sponsor Contact: [name].
Theracos Sub, LLC
[name]
[name]

Sponsor Protocol Representative: [name].
[name]
[contact], [contact]
e-mail: [contact]

Medical Monitor: [name].
[name]
[contact], [contact]
Email: [contact]

Date

Version 2.0: 13 June 2017

Confidentiality Statement

The information contained in this protocol is confidential and provided only to the investigators, clinical study collaborators, investigational drug managers, study sites and institutional review boards participating in the study. The information may, therefore, not be disclosed to any third party except for subjects when receiving their consent, or used for purposes other than this study without the written consent of Theracos Sub, LLC

SYNOPSIS

Sponsor: Theracos Sub, LLC

Name of Finished Product: Bexagliflozin Tablets, 20 mg

Name of Active Ingredient: Bexagliflozin

Name of Inactive Ingredient:

Polyethylene oxide, glyceryl behenate, lactose monohydrate, micronized poloxamer 188, microcrystalline cellulose, colloidal silicon dioxide, and magnesium stearate (vegetable grade). The tablets are film-coated with Opadry II Blue with no markings on the tablets.

Study Title:

A Phase 1, Open-label, Randomized, Two-period, Two-treatment, Crossover Study to Evaluate the Effect of Bexagliflozin on the Pharmacokinetics of Digoxin in Healthy Subjects

Study Number: THR-1442-C-443

Study Phase: 1

Primary Objective:

To evaluate the effect of bexagliflozin on the pharmacokinetics (PK) of digoxin

Secondary Objective:

To assess the safety and tolerability of digoxin when it is co-administered with bexagliflozin

Study Design:

This is a phase 1, single center, open-label, two-period, two-treatment, crossover study to evaluate the effect of bexagliflozin tablets, 20 mg, on the pharmacokinetics of digoxin, 0.5 mg, when co-administered in healthy subjects. Approximately 18 eligible healthy subjects will be randomized to one of the two groups (Group 1 and 2) with up to 9 subjects per group. Subjects will reside in the clinic for a total of 16 days, divided into two treatment periods, Periods 1 and 2. Subjects will be discharged and out of the clinic between the 2 treatment periods for 9 days for Group 1 and 7 days for Group 2. During the treatment periods, subjects will receive 2 treatments in differing order: Treatment A, bexagliflozin administered once daily for 8 days with digoxin co-administered on Day 3 and Treatment B, digoxin administered alone on Day 1. Safety monitoring will be conducted throughout the study.

Group 1:

Period 1, Treatment A: Subjects randomized to Group 1 will be admitted to the clinic on Day 0. Starting on Day 1, subjects will receive once daily oral dose of 20 mg bexagliflozin for 8 days; a single dose of 0.5 mg digoxin will be co-administered with bexagliflozin on Day 3. Blood samples for PK will be drawn at pre-dose and at 0.5, 1, 1.5, 2, 3, 4, 6, 8, and 12 hours (h) on Day 3, 24 h (Day 4), 48 h (Day 5), 72 h (Day 6), 96 h (Day 7), and 120 h (Day 8) after administration of digoxin. Subjects will be discharged on Day 8.

Period 2, Treatment B: Subjects will be admitted on Day 18 and receive a single oral dose of 0.5 mg digoxin on Day 19. Blood samples for PK will be drawn at pre-dose and at 0.5, 1, 1.5, 2, 3, 4, 6, 8, and 12 hours (h) on Day 19, 24 h (Day 20), 48 h (Day 21), 72 h (Day 22), 96 h (Day 23), and 120 h (Day 24) after administration of digoxin. Subjects will be discharged

from the clinic on Day 24.

Group 2:

Period 1, Treatment B: Subjects randomized to Group 2 will be admitted to the clinic on Day 0. On Day 1, subjects will receive a single oral dose of 0.5 mg digoxin. Blood samples for PK will be drawn at pre-dose and at 0.5, 1, 1.5, 2, 3, 4, 6, 8, and 12 hours (h) on Day 1, 24 h (Day 2), 48 h (Day 3), 72 h (Day 4), 96 h (Day 5), and 120 h (Day 6) after administration of digoxin. Subjects will be discharged on Day 6.

Period 2, Treatment A: Subjects will be admitted on Day 14. On Day 15, subjects will start to receive once daily oral dose of 20 mg bexagliflozin for 8 days; a single dose of 0.5 mg digoxin will be co-administered with bexagliflozin on Day 17. Blood samples for PK will be drawn at pre-dose and at 0.5, 1, 1.5, 2, 3, 4, 6, 8, and 12 hours (h) on Day 17, 24 h (Day 18), 48 h (Day 19), 72 h (Day 20), 96 h (Day 21), and 120 h (Day 22) after administration of digoxin. Subjects will be discharged from the clinic on Day 22.

Study Population: Approximately 18 healthy subjects are planned.

Diagnosis and Main Criteria for Inclusion:

1. Subjects who are between the ages of 18 and 55 years, inclusive, in good health based on medical history, physical examination, ECG, and routine laboratory tests (blood chemistry, electrolytes, hematology, lipids, urinalysis, and drug screen)
2. Subjects with body-mass index (BMI) between 18.0 kg/m² and 32.0 kg/m², inclusive
3. Subjects who are not surgically sterile must agree to use appropriate birth control when engaging in sexual intercourse for a period of 30 days after discharge from the clinic
4. Subjects who are non-smokers for at least 6 months prior to screening

Test Product; Dose; and Mode of Administration:

Bexagliflozin Tablets, 20 mg, oral administration

Reference Therapy; Dose; and Mode of Administration:

Digoxin Tablets, 0.5 mg, oral administration

Duration of Treatment:

Each study subject will receive a total of 8 doses of bexagliflozin (20 mg) and 2 doses of digoxin (0.5 mg) during 2 treatment periods with a study duration of up to 46 days, including screening and washout periods.

Pharmacokinetic Variables:

The following PK parameters of digoxin, if possible, will be determined after each subject is dosed with either digoxin alone, or the combination of digoxin and bexagliflozin.

C _{max}	Maximum observed plasma concentration
t _{max}	Time of maximum observed plasma concentration
λ _z	Terminal elimination phase rate constant
t _½	Apparent terminal elimination half-life
CL/F	Apparent oral clearance
V _z /F	Apparent volume of distribution

AUC_{0-t} Area under the plasma concentration-time curve from Time 0 to Time t (time of last quantifiable plasma concentration)

$AUC_{0-\infty}$ Area under the plasma concentration-time curve from Time 0 to infinity

Safety Assessments:

Physical examinations

Vital signs

12-lead electrocardiograms

Clinical laboratory tests including blood chemistry and hematology parameters

Urinalysis

Adverse events

Concomitant medication use

Statistical Methods:

Statistical analysis will be performed using Statistical Analysis Software SAS for Windows[®] (SAS, USA). PK parameters of digoxin will be calculated by non-compartmental analyses (NCA) of plasma concentration-time data using Phoenix[®] WinNonlin[®] 6.4 (Certara, USA). To assess the effect of bexagliflozin on the PK of digoxin, an analyses of variance (ANOVA) using a linear mixed-effects model will be fitted to the natural logarithmic transformation of PK parameters of digoxin (C_{max} , AUC_{0-t} and $AUC_{0-\infty}$). The linear mixed-effects model will include subject as a random effect, and treatment, period, and sequence as fixed effects. The 90% confidence intervals will be constructed for the (digoxin with bexagliflozin) to (digoxin alone) ratio of the least squares (LS) geometric means of PK parameters (C_{max} , AUC_{0-t} and $AUC_{0-\infty}$), with 80-125% defined as the lack of interaction boundaries.

Descriptive statistics for the PK parameters C_{max} , T_{max} , $AUC_{0-\infty}$, AUC_{0-t} , CL/F , V_z/F , λ_z and $T_{1/2}$ will be tabulated by treatment. Means, standard deviations, medians, ranges (min, max) and geometric means and coefficients of variation will be presented for all PK parameters with exception of T_{max} . Medians and ranges will be presented for T_{max} .

Date of Original Protocol: 09 June 2017

Date of Most Recent Protocol V.2.0: 13 June 2017

Prepared in: Microsoft Word 2007

TABLE OF CONTENTS

SYNOPSIS.....	2
LIST OF ABBREVIATIONS AND DEFINITIONS OF TERMS.....	9
1 INTRODUCTION	11
2 STUDY OBJECTIVES.....	12
2.1 Primary Objective	12
2.2 Secondary Objective	12
3 INVESTIGATIONAL PLAN.....	13
3.1 Overall Study Design and Plan.....	13
3.1.1 Group 1	13
3.1.2 Group 2	13
3.2 Rationale for Study Design and Control Group.....	14
3.2.1 Rationale for Study Design.....	14
3.2.2 Rationale for Dose Selection	15
3.2.3 Rationale for PK Sampling Time Points.....	15
3.3 Study Duration and Dates	15
4 STUDY POPULATION SELECTION	17
4.1 Study Population.....	17
4.2 Inclusion Criteria	17
4.3 Exclusion Criteria	18
5 STUDY TREATMENT(S).....	20
5.1 Description of Treatment(s).....	20
5.1.1 Investigational Product: Bexagliflozin	20
5.1.2 Cardiovascular Drug: Digoxin.....	20
5.2 Treatment(s) Administered.....	20
5.3 Selection and Timing of Dose for Each Subject.....	20

UGT1A9	uridine diphosphate glucuronosyltransferase isoform 1A9
ULN	upper limit of normal
UTI	urinary tract infection
t_{\max}	time to maximum plasma concentration
$t_{1/2}$	apparent terminal elimination half-life
US	United States
V_z/F	apparent volume of distribution
WBC	white blood cell (count)
WHO-DD	World Health Organization Drug Dictionary

1 INTRODUCTION

Bexagliflozin is a candidate OHA that is a potent and highly specific inhibitor of SGLT2. (Zhang et al., 2011). Bexagliflozin has been shown to cause dose-dependent increases in urinary glucose excretion (UGE) in humans, rats, dogs and monkeys and to reduce HbA1c in animal models of T2DM and in diabetic subjects. Bexagliflozin is cleared predominantly by metabolism to an inactive metabolite, bexagliflozin 3-O-glucuronide by the uridine diphosphate glucuronosyltransferase isoform 1A9 (UGT1A9) pathway. Detailed information regarding bexagliflozin metabolism, clinical studies and potential risks for study subjects are provided in the Investigator's Brochure.

In vitro studies showed bexagliflozin is a substrate for P-glycoprotein (P-gp) and inhibits P-glycoprotein (P-gp) mediated transport with an IC₅₀ of 3.7 µM. P-gp is one of the drug transporters that determine the uptake and efflux of a range of drugs. Drugs that inhibit P-gp can interact with other drugs transported by the pump and therefore affect the exposure of other co-administered drugs that are P-gp substrates.

Digoxin is a P-gp substrate (Tanigawara et al., 1992) that may be co-administered with bexagliflozin. Since individuals with T2DM have an increased risk of heart failure (Nichols et al., 2001) and atrial fibrillation (Nichols et al., 2009), patients with diabetes and hypertension often require treatment with cardiac glycosides such as digoxin. Digoxin has been used for over 2 centuries to treat heart failure and atrial fibrillation. Digoxin acts as a positive inotropic agent by inhibiting the sodium-potassium adenosine triphosphatase (ATPase), causing an increase in myocardial contractility (US FDA, 2002). Digoxin is excreted largely unchanged in urine and bile.

Due to the narrow therapeutic index of digoxin (Smith et al., 1969), small changes in absorption, bioavailability, or clearance of the drug could lead to decreased therapeutic effect or toxicity. Therefore, this study aims to evaluate the effects of co-administered bexagliflozin on the pharmacokinetics of digoxin.

2 STUDY OBJECTIVES

2.1 Primary Objective

The primary objective of this study is to evaluate the effect of bexagliflozin on the pharmacokinetics (PK) of digoxin after co-administration.

2.2 Secondary Objective

The secondary objective of this study is to evaluate the safety and tolerability of digoxin when co-administered with bexagliflozin.

3 INVESTIGATIONAL PLAN

3.1 Overall Study Design and Plan

This is a phase 1, single center, open-label, two-treatment period, crossover study to evaluate the effect of bexagliflozin tablets, 20 mg, on the PK of digoxin, 0.5 mg after co-administration in healthy subjects. Approximately 18 eligible healthy subjects who consent to the study will be enrolled into the study and randomized to one of the two groups with up to 9 subjects per group. Each subject will participate in 2 periods during which subjects will receive 2 treatments (Treatment A: bexagliflozin co-administered with digoxin, Treatment B: digoxin alone). During the duration of the study, each subject will receive 8 single doses of bexagliflozin and 2 single doses of digoxin.

3.1.1 Group 1

Approximately 9 subjects will be admitted to the clinic on Day 0 and will receive the following study drugs in two treatment periods:

Period 1, Treatment A

Subjects will receive a single oral dose of 20 mg bexagliflozin tablet daily starting on Day 1 for 8 days, and a single oral dose of 0.5 mg digoxin will be co-administered with bexagliflozin on Day 3. Blood samples for PK will be drawn at pre-dose and at 0.5, 1, 1.5, 2, 3, 4, 6, 8, and 12 hours (h) on Day 3, 24 h (Day 4), 48 h (Day 5), 72 h (Day 6), 96 h (Day 7), and 120 h (Day 8) after administration of digoxin. Subjects will be discharged on Day 8 after all study activities are completed.

Period 2, Treatment B

Subjects will be admitted on Day 18. On Day 19, subjects will receive a single oral dose of 0.5 mg digoxin. Blood samples for PK will be drawn at pre-dose and at 0.5, 1, 1.5, 2, 3, 4, 6, 8, and 12 hours (h) on Day 19, 24 h (Day 20), 48 h (Day 21), 72 h (Day 22), 96 h (Day 23), and 120 h (Day 24) after administration of digoxin. Subjects will be discharged on Day 24 after all study activities are completed.

Clinical laboratory tests and safety monitoring will be conducted during Periods 1 and 2.

3.1.2 Group 2

Approximately 9 subjects will be admitted to the clinic on Day 0 and will receive the following study drugs in two treatment periods:

Period 1, Treatment B

Subjects will receive a single oral dose of 0.5 mg digoxin on Day 1. Blood samples for PK will be drawn at pre-dose and at 0.5, 1, 1.5, 2, 3, 4, 6, 8, and 12 hours (h) on Day 1, 24 h

(Day 2), 48 h (Day 3), 72 h (Day 4), 96 h (Day 5), and 120 h (Day 6) after administration of digoxin.

Period 2, Treatment A

Subjects will be admitted on Day 14. Subjects will receive a single oral dose of 20 mg bexagliflozin daily for 8 days starting on Day 15, and a single oral dose of 0.5 mg digoxin will be co-administered with bexagliflozin on Day 17. Blood samples for PK will be drawn at pre-dose and at 0.5, 1, 1.5, 2, 3, 4, 6, 8, and 12 hours (h) on Day 17, 24 h (Day 18), 48 h (Day 19), 72 h (Day 20), 96 h (Day 21), and 120 h (Day 22) after administration of digoxin. Subjects will be discharged on Day 22 after all study activities are completed.

Clinical laboratory tests and safety monitoring will be conducted during Periods 1 and 2.

For overall study design and dosing schedule, see the Study Design in Figure 1 and the Dosing Schedule in [Appendix 2](#).

[figure not shown]

Figure 1 Study Design

3.2 Rationale for Study Design and Control Group

3.2.1 Rationale for Study Design

The primary goal of the study is to test the effect of bexagliflozin on the PK of digoxin. The two treatment period, crossover design will allow the PK of digoxin to be studied with and without the co-administration of bexagliflozin. This design was chosen to properly separate treatment effects from period effects.

Bexagliflozin is cleared predominantly by metabolism to an inactive metabolite, bexagliflozin 3-O-glucuronide by uridine diphosphate glucuronosyltransferase isoform 1A9 (UGT1A9) pathway. *In vitro* metabolism studies demonstrated that bexagliflozin is not a

potent inhibitor or inducer of CYP450 enzymes. In the urine, unchanged parent drug accounted for less than 2% of the dose. *In vitro* studies showed bexagliflozin is a substrate for P-glycoprotein (P-gp) and inhibits P-gp mediated transport with an IC_{50} of 3.7 μ M. P-gp is one of the drug transporters that determine the uptake and efflux of a range of drugs. Drugs that inhibit P-gp can interact with other drugs transported by the pump and therefore affect the exposure of other co-administered drugs that are P-gp substrates.

Digoxin is a P-gp substrate that may be co-administered with bexagliflozin. The co-administration of digoxin with P-gp modulators could result in marked changes in the renal elimination of digoxin. Meanwhile, digoxin has a narrow therapeutic index and small changes in absorption, bioavailability, or clearance of the drug could lead to decreased therapeutic effect or toxicity.

This study is designed to evaluate the extent of the effect of bexagliflozin (a potential P-gp inhibitor) on the PK of digoxin (a P-gp substrate). The study results are important for the safe and effective use of digoxin and bexagliflozin.

3.2.2 Rationale for Dose Selection

Bexagliflozin produces a dose-dependent, saturable increase in urinary glucose excretion (UGE) in healthy volunteers and diabetic subjects. Population pharmacodynamic modeling has indicated that bexagliflozin doses of 20 mg result in 90% of the maximal UGE and the bexagliflozin tablet, 20 mg will be the commercial product.

The dosage for digoxin, 0.5 mg, was chosen as it is a safe and effective dose that is in between an acute treatment dose and maintenance treatment dose for a 70 kg adult. The dose is considered a safe dose at which possible drug-drug interactions and plasma concentrations of digoxin can be detected.

3.2.3 Rationale for PK Sampling Time Points

The $T_{1/2}$ of bexagliflozin is 7.80 to 9.71 h, while the $T_{1/2}$ of digoxin is significantly longer at approximately 35 h. Due to the long half-life of digoxin, the study is designed so that PK samples are collected up to 7 half-lives of digoxin. A minimum duration of 16 days (~11 half-lives of digoxin) is required between the two digoxin administrations to ensure the wash-out period is sufficiently long.

For Treatment A, digoxin will be administered on Day 3 after 2 days (~5 half-lives of bexagliflozin) of dosing with bexagliflozin. It is predicted that steady state of bexagliflozin will have been achieved at that time.

3.3 Study Duration and Dates

Subjects will be screened within 21 days prior to the start of enrollment. Eligible subjects who consent to the study will be randomized to one of two treatment groups (Group 1 and Group 2). Each treatment group will receive 2 treatments (Treatment A and Treatment B) in a different order during each of the treatment periods (Period 1 and Period 2). The duration

of Treatment A is 9 days and Treatment B is 7 days. Subjects will remain in the clinic for 16 days during the entire study. Subjects will be out of the clinic between the 2 treatment periods for 9 days for Group 1 and 7 days for Group 2. Overall, each study subject will receive 8 single oral doses of 20 mg bexagliflozin tablets and 2 single oral doses of 0.5 mg digoxin in each treatment period. The duration of the overall study from screening until study termination is estimated to be a maximum of 46 days.

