5.1.2 Cardiovascular Drug: Digoxin

Digoxin is a cardiac glycoside that mediates its effects on Na/K ATPase to increase cardiac output. Majority of digoxin is excreted in urine and bile unchanged, and metabolism of digoxin appears to be minimal (Iisalo, 1977). After oral administration, the absorption of digoxin is mediated by P-glycoprotein (P-gp). 0.25 mg digoxin tablets are white, round tablets with an imprint code JSP-545. 0.25 mg digoxin tablets are the highest available tablet dose, and two 0.25 mg tablets will be taken q.d. for this study.

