5.2 Treatment(s) Administered

Each study subject will be administered 8 single oral doses of bexagliflozin tablet, 20 mg and 2 single oral doses of 0.5 mg digoxin in 2 treatment periods. See [Appendix 2](#) for the Dosing Schedule.

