6.3.2 Extent of Exposure to Study Medication

Subjects who gave consent to participate in the study will be randomly assigned to 1 of the 2 treatment groups (Group 1 and Group 2). Each treatment group will receive 2 treatments (Treatment A and Treatment B) in a different order during each of the treatment periods (Period 1 and Period 2). The duration of

Treatment A is 9 days and Treatment B is 7 days. Subjects will remain in the clinic for 16 days during the entire study. Subjects will be out of the clinic between the 2 treatment periods for 9 days for Group 1 and 7 days for Group 2. Overall, each study subject will receive 8 single oral doses of 20 mg bexagliflozin tablets and 2 single oral doses of 0.5 mg digoxin in each treatment period. The duration of the overall study from screening until study termination is to be a maximum of 46 days.

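### Do Protocol 3.3 and SAP 6.3.2 put the number of study drug doses per subject in doubt?

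*Protocol*

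**What the plan says.** Protocol 3.3 (Study Duration and Dates) ends its description of the two periods by giving each subject "8 single oral doses of 20 mg bexagliflozin tablets and 2 single oral doses of 0.5 mg digoxin in each treatment period". SAP 6.3.2 (Extent of Exposure to Study Medication) carries the same text, including "2 single oral doses of 0.5 mg digoxin in each treatment period".

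Elsewhere the same two numbers are totals for the study:

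- Protocol synopsis, Duration of Treatment: "a total of 8 doses of bexagliflozin (20 mg) and 2 doses of digoxin (0.5 mg) during 2 treatment periods".
- Protocol 3.1: over the study, "each subject will receive 8 single doses of bexagliflozin and 2 single doses of digoxin". SAP 3.1 says the same.
- Protocol 5.2: "2 single oral doses of 0.5 mg digoxin in 2 treatment periods", with a pointer to the dosing schedule in Appendix 2.

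The synopsis describes the reference arm as "Treatment B, digoxin administered alone on Day 1". Protocol 3.2.3 adds: "A minimum duration of 16 days (~11 half-lives of digoxin) is required between the two digoxin administrations".

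Separately, the product description in Protocol 5.1.2 says that "two 0.25 mg tablets will be taken q.d. for this study". The protocol's abbreviation list expands *q.d.* as once daily.

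**The concern.** Read word for word, Protocol 3.3 and SAP 6.3.2 double the exposure to both drugs and place bexagliflozin in the period meant to show digoxin alone. If that were the intended dosing, the treatment contrast would no longer be digoxin with bexagliflozin against digoxin alone. The single-dose pharmacokinetic parameters would also be contaminated by a second digoxin dose in the same period.

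The *q.d.* in Protocol 5.1.2 could likewise be taken to mean daily digoxin. The protocol itself calls digoxin a drug of narrow therapeutic index, so conflicting statements of how often it is given deserve a check. The SAP also contradicts itself, 3.1 against 6.3.2, and 6.3.2 is the section a reader would open for exposure.

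**Working it through.** **Inputs.** Dosing days come from Protocol 3.1.1, 3.1.2, 7.2, 7.3 and Appendix 2, which agree with one another.

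| Group | Period | Bexagliflozin days | Digoxin day | Count (bexagliflozin / digoxin) |
|---|---|---|---|---|
| 1 | 1 (Treatment A) | 1–8 | 3 | 8 / 1 |
| 1 | 2 (Treatment B) | none | 19 | 0 / 1 |
| 2 | 1 (Treatment B) | none | 1 | 0 / 1 |
| 2 | 2 (Treatment A) | 15–22 | 17 | 8 / 1 |

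**Step 1: reproduce the whole-study figure.** Group 1: 8 + 0 = 8 bexagliflozin and 1 + 1 = 2 digoxin. Group 2: 0 + 8 = 8 and 1 + 1 = 2. The schedule returns the totals in the synopsis, Protocol 3.1 and 5.2, and SAP 3.1. Digoxin per subject is 2 × 0.5 mg = 1.0 mg.

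**Step 2: the literal per-period reading.** Bexagliflozin 8 × 2 = 16; digoxin 2 × 2 = 4, or 4 × 0.5 mg = 2.0 mg. No period in either group holds 8 bexagliflozin and 2 digoxin doses.

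**Step 3: can the literal reading be carried out?**

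- *Room in Treatment B.* Protocol 3.3 itself gives Treatment B 7 days. From dosing to discharge there are 24 − 19 + 1 = 6 days in Group 1 and 6 − 1 + 1 = 6 in Group 2. Eight once-daily doses do not fit.
- *Separation of digoxin doses.* The scheduled gaps are 19 − 3 = 16 days and 17 − 1 = 16 days, equal to the stated minimum. With the protocol's half-life of about 35 h, 16 × 24 / 35 = 10.97, which reproduces its figure of roughly 11 half-lives. Two digoxin doses in one period could be at most 8 − 1 = 7 days apart under Treatment A (also 22 − 15 = 7), or 24 − 19 = 5 days under Treatment B (also 6 − 1 = 5). Both are short of 16.

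So the per-period reading is incompatible with Protocol 3.2.3, and with the treatment length given in the same paragraph of 3.3.

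**Step 4: the once-daily abbreviation.** Protocol 5.1.2 describes the product. It says 0.25 mg is the largest available tablet, and 2 × 0.25 mg = 0.5 mg, the dose per administration used throughout. The sentence names no days and no duration, so no alternative dose total follows from it. It can be read as one two-tablet intake on a dosing day. The scheduling sections all show one digoxin administration per period.

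**Step 5: does any analysis use the count?** SAP 6.3.2 defines no exposure variable, and SAP Section 8 lists no exposure summary. SAP 7.2 computes CL/F and Vz/F from the dose of a single administration, on which the documents agree. SAP 6.3.3 assigns adverse events by the first dose in each period, not by the number of doses. The mixed model uses treatment, period, sequence and subject.

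**The case for a change.** The strongest case for acting is that this is a dosing statement for a drug of narrow therapeutic index, repeated in two documents. Protocol 10.4 has the investigator draft the consent form from the protocol, so the phrase could travel further. Under the letter of 3.3, every subject dosed according to Appendix 2 would be a deviation, and Protocol 10.8 requires violations to be reported. SAP 6.3.2 offers no other count to correct the reader, and rewording three sentences costs almost nothing.

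Part of this stands. The statements do conflict, and the sponsor should confirm the intended wording so that one count and one description of digoxin administration appear throughout. The *q.d.* point is separate and weaker, but it belongs in the same tidy-up.

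The rest does not carry over to conduct or results. Protocol 3.3 concerns duration and dates; administration is set out in 5.2, 5.3, 7.2, 7.3 and Appendix 2. Protocol 5.8 has all dosing supervised in the clinic with exact times recorded. The 16-dose and 4-dose totals describe a regimen that the protocol's own schedule rules out, so they show how visible the inconsistency is and do not measure an exposure at risk.

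**Conclusion.** No change to the design or analysis follows. This is an inconsistency of wording with the marks of a drafting slip. The sentence opens with *Overall*, its figures equal the whole-study totals, and Protocol 5.2 has a nearly identical sentence that refers to the 2 treatment periods together. On paper the discrepancy is 16 against 8 bexagliflozin doses and 4 against 2 digoxin doses. In the schedule it is zero, because both groups count to 8 and 2.

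The randomization, sampling times, pharmacokinetic derivations, mixed model, 90% confidence intervals and 80–125% boundaries are the same however the phrase is worded. Reconciling Protocol 3.3, Protocol 5.1.2 and SAP 6.3.2 with the other sections is editorial and rests with the sponsor.

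This conclusion assumes that sites dose from the day-by-day activities and Appendix 2, as the protocol's structure implies, and that the separate table shells, which are not part of these documents, derive exposure from recorded administrations and not from the sentence in SAP 6.3.2.
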